6. SAMPLE SIZE

6.1 Preliminary Data

Sample size estimates were informed by preliminary data from a pilot of the ESTEEM study ([name] et al. 2015), in which we saw a 60% reduction in the primary outcome at 6 months in the ESTEEM arm compared to waitlist control.

6.2 Sample Size Determination for the Primary Outcome

Sample size calculations were carried out using PASS 12 for logistic regression.

Our primary goal is to demonstrate a greater reduction at 8 months in condomless anal sex in the absence of either PrEP or known undetectable viral load of HIV+ primary partners, in the ESTEEM arm versus the CMHT and VCT-only arms. In our pilot study, we saw a 60% reduction in condomless anal sex at 6 months in the ESTEEM arm. We used these estimates to inform our 8-month endpoint.

Based on previous studies of VCT and the fact that CMHT does not specifically focus on condomless anal sex, we expect that these arms will yield lower reductions compared to ESTEEM, but a slightly larger reduction in CMHT (20%) compared to VCT-only (15%). To achieve at least 90% power at a 5% type I error rate, accounting for an R-square of 0.1 between treatment arm and the covariates (e.g., site, race/ethnicity), we will need 80 individuals in the ESTEEM and CMHT arms, and 40 individuals in the VCT-only arm. Although we plan to take steps to increase our retention rate from our pilot study, we conservatively estimate the retention at 8 months to be 80%. Therefore, we planned to randomize 100 ESTEEM, 100 CMHT, and 50 VCT-only young gay and bisexual men. The original target sample size was 250 participants enrolled from the two study sites [New York: 150 (60 ESTEEM, 60 CMHT, 30 VCT) and Miami: 100 (40 ESTEEM, 40 CMHT, 20 VCT)]. This was increased to 254 on 2/28/18 to correct an imbalance in the 2:2:1 randomization. The final sample size was 254.

6.3 Power for Secondary Outcomes

For secondary outcomes (e.g., mental health, substance use), we will have 80% power to detect an effect size of 0.55 and 0.70 for ESTEEM vs. CMHT and ESTEEM vs. VCT-only, respectively, at a type I error rate of 0.01 (conservative due to multiple testing). These effect sizes are smaller than those found in the pilot ([name] et. al. 2015).

6.4 Power for Tertiary Outcomes

STATISTICAL ANALYSIS PLAN

Power analyses were not conducted to inform tertiary outcomes.

7 INTERIM MONITORING

7.1 Overview

Interim monitoring focused on patient accrual, baseline comparability of treatment groups, protocol adherence, loss to follow-up, data completeness and quality, safety, efficacy, and futility. The summary of the types of tables, listing and figures (TLFs) generated for semi-annual open and closed DSMB reports is presented in Appendix A.

7.2 Safety

Details of the safety and adverse event monitoring plan were provided in study protocol. The principal investigator was responsible for monitoring the data and assuring protocol compliance. Unanticipated problems involving risks to subjects or others, including adverse events, were followed by a written report within five calendar days of the principal investigator becoming aware of the event to the institutional review board (IRB). The principal investigator apprised fellow investigators and study personnel of all unanticipated problems and adverse events that occurred during the conduct of this research project. The protocol's data safety monitoring board (DSMB) was informed of serious or unanticipated adverse events. Presented to the DSMB at each annual interim meeting were the following summaries by time point: HIV status, incidence of chlamydia and gonorrhea, TLFB reports of risky sexual behavior (total sex acts, total sex acts under the influence and condomless anal sex acts), and summaries of depression and suicidality scores (HAM-D and SIDAS respectively). These reports were presented across treatment arms in aggregate in an 'open meeting' with the study team present, followed by an unblinded presentation of these data by treatment arm to the DSMB by the unblinded statistician.

8 ANALYTIC PLAN

8.1 Overview

The analysis of the primary and secondary outcomes will be according to the principle of intent-to-treat, i.e., participants will be analyzed according to their original treatment assignment regardless of adherence to protocol. All analyses will include the participant as the unit of analysis. SAS 9.4, SPSS 26.0, MPlus 8.4, and the latest version of R (currently 4.0.2) software will be used for all analyses.

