each appointment and allows them to answer the questions where they feel most comfortable. Survey questions assessing suicidality will be completed in office under the supervision of a clinical staff member for the baseline 2 and follow up assessment visits. When scheduling any 4-month, 8-month, and 12-month remote follow-up assessment, prior to the appointment a trained study staff member will request participant address via email and locate the nearest emergency services. While assessing suicidality, if there is a concern for safety, just as with any participant seen in the offices, the study staff will contact the nearest emergency services and adhere to the remainder of the established clinical protocol.

ESTEEM treatment will take place over 10 sessions delivered in our offices. All participants, including those randomized to receive VCT only, will receive VCT during the baseline 1 and 12 month follow up appointments, which will take place over one session in our offices. Participants assigned to receive CMHT will receive 10 sessions of CMHT at the Institute for Human Identity (NYC) or Care Resources (Miami). CMHT is not prescribed in our treatment manuals, but is instead delivered by community providers as they usually provide treatment. These two sites are known for providing LGBT-affirmative treatment in safe, supportive environments. ESTEEM and CMHT sessions will be videotaped in the settings where they are delivered [i.e., the Institute for Human Identity (NYC) or Care Resources (Miami)] and both therapists and participants will complete short surveys after each therapy session at the appointment site; all assessments will be completed in our research offices and at home for the baseline 1, baseline 2, 4-month, 8-month, and 12-month assessment visits. Tapes of CMHT sessions will be immediately retrieved from the video recording devices at the CMHT offices by study staff and provided to PI [name] via secure server.

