### **CMHT Therapist Participants:**

Therapists at our CMHT sites will be considered participants in the study, as they will be videotaped and will complete short assessments after each therapy session. We will also collect demographic information about each therapist, including race, sexual orientation, and years of work experience from the CMHT therapists prior to their meeting with therapy participants. To be included as participants in the study, CMHT therapists must be currently providing therapy on an ongoing basis at the CMHT sites (Institute for Human Identity in New York City and Care Resources in Miami).

5. **Describe** how access to the population will be gained in the study.

We will use active and passive recruitment strategies. Active approaches will involve conducting eligibility screening via electronic tablet at bars/clubs and support groups (e.g., coming out groups and 20-somethings group at the NYC LGBT Center). Passive approaches will involve advertising on YGBM-oriented mobile apps and websites (e.g., Grindr, Scruff, BGCLive, Growlr), clinic waiting rooms (e.g., Callen-Lorde Community Health Center, college counseling centers), YGBM-focused media (e.g., Craigslist, Facebook, Reddit, party listservs), and referrals from previous or current study participants. As part of passive recruitment we will also contact participants from previous research studies who consented to be contacted for future studies. Advertisements will engage help-seeking YGBM by emphasizing the study as a safe venue for discussing sex and HIV.

CMHT therapists will be identified by directors at our CMHT partner sites.

6. **Participant classification:** Check off all classifications of participants that will be specifically recruited for enrollment in the research project. Will participants who may require additional safeguards or

other considerations be enrolled in the study? If so, identify the population of participants requiring special safeguards and provide a justification for their involvement.

- Children
- Healthy
- Non-English Speaking
- Prisoners
- Economically disadvantaged
- Decisionally Impaired
- Employees
- Pregnant women
- Yale Students
- Other vulnerable population (who?):
- Psychology Pool

NOTE: Is this research proposal designed to enroll children who are wards of the state as potential participants?  Yes  No (If yes, see HRPP Policy 310.4 for further requirements)

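### No planned analysis or power figure allows for participants in the ESTEEM and CMHT arms sharing therapists, which matters mainly for ESTEEM vs CMHT if the therapist ICC is positive

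*SAP*

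**What the plan says.** **How the arms are delivered.** Protocol Section IV, item 3 describes ESTEEM as ten individual CBT sessions. It describes CMHT as ten sessions given by community clinicians at one clinic per city, without a study manual. All arms receive VCT before randomization, and VCT-only participants then receive nothing more. Two arms are therefore nested in therapists and the third is not. The number of therapists is not given for either arm.

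**What is recorded.** For ESTEEM and CMHT sessions the protocol says "both therapists and participants will complete short surveys after each therapy session". It adds that "Therapists at our CMHT sites will be considered participants in the study", with their demographic details collected.

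**How it is analysed.** SAP 8.1: "All analyses will include the participant as the unit of analysis". Sections 8.3.1 and 8.3.2 use generalized linear mixed models and 8.4.2.1 a linear mixed model. Adjustment is for site, for the baseline value in 8.3.2 and 8.4.2.1, and for race/ethnicity in the method cell of 8.3.1. Random effects are not listed. No section names a therapist effect, an ICC or cluster-robust variance.

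**How it is powered.** SAP 6.2 allows for an R-square of 0.1 with covariates and for 80% retention. Section 6.3, with alpha set at 0.01, says of the secondary outcomes: "we will have 80% power to detect an effect size of 0.55 and 0.70 for ESTEEM vs. CMHT and ESTEEM vs. VCT-only, respectively".

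**The concern.** Participants treated by the same therapist may have more similar outcomes than participants treated by different ones. An analysis that leaves this out treats chance differences between two sets of therapists as if they were participant-level noise, averaged over the full sample. The result is confidence intervals that are too narrow and p-values that are too small.

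ESTEEM vs CMHT is the most exposed comparison because both arms are clustered; in ESTEEM vs VCT-only, one arm is. Adjusting for site does not remove variation between therapists within a site and arm. ESTEEM vs CMHT is also the comparison the protocol (Aim 1) relies on to show the benefit of the transdiagnostic approach, and it is the second step of the primary testing sequence. The secondary power figures would be affected in the same way.

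**Working it through.** **Inputs from the documents.** SAP 6.2: "we will need 80 individuals in the ESTEEM and CMHT arms, and 40 individuals in the VCT-only arm". SAP 6.3: effect sizes d of 0.55 and 0.70, alpha 0.01. Section 6.3 does not state sidedness; two-sided is assumed, as in the SAP 8 tables.

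**Assumptions.** ICC 0.02 to 0.05; k = 16, 10 or 5 therapists per arm, so m = 80/k = 5, 8 or 16 evaluable participants each. Neither quantity is in the documents.

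**1. Reproduce the stated power, participants independent.** Power = Phi(d / sqrt(V) - 2.576), with V = 1/n1 + 1/n2 and SD = 1.
- ESTEEM vs CMHT: V = 1/80 + 1/80 = 0.025; 0.55/0.1581 - 2.576 = 0.903; power 81.7% (80.7% by noncentral t).
- ESTEEM vs VCT-only: V = 1/80 + 1/40 = 0.0375; 0.70/0.1936 - 2.576 = 1.039; power 85.1% (83.8% by noncentral t).

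The first matches the stated 80%. The second is 4-5 points above it, so that figure is conservative.

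**2. Add therapist clustering.** The design effect is DE = 1 + (m - 1) x ICC, applied to ESTEEM and CMHT but not to VCT-only. So V becomes 2 x DE/80 for CMHT, and DE/80 + 1/40 for VCT-only. Power is for a test with the correct variance at alpha 0.01. The true type I error of a test that ignores therapists at nominal 5% is 2 x [1 - Phi(1.96 x sqrt(V at DE = 1 / V))].

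| k | m | ICC | DE | Type I, vs CMHT | Type I, vs VCT | Power, d=0.55 vs CMHT | Power, d=0.70 vs VCT |
|---|---|---|---|---|---|---|---|
| 16 | 5 | 0.02 | 1.08 | 5.9% | 5.3% | 78.0% | 83.9% |
| 16 | 5 | 0.05 | 1.20 | 7.4% | 5.8% | 72.6% | 82.2% |
| 10 | 8 | 0.02 | 1.14 | 6.6% | 5.5% | 75.2% | 83.1% |
| 10 | 8 | 0.05 | 1.35 | 9.2% | 6.4% | 66.2% | 80.1% |
| 5 | 16 | 0.02 | 1.30 | 8.6% | 6.2% | 68.3% | 80.8% |
| 5 | 16 | 0.05 | 1.75 | 13.8% | 8.0% | 52.1% | 74.5% |

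In the row k = 10, ICC 0.05, t-based power is about 65% vs CMHT and 78.7% vs VCT-only. Simulation with ordinary t-tests (20,000 trials per setting) gave 6-8% type I error vs CMHT at ICC 0.02 and 8-14% at 0.05, in line with the formula. For a binary outcome with a latent-scale ICC of 0.05 it gave 6-10%.

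**3. Slack.** 80% power needs d / sqrt(V) of at least 2.576 + 0.842 = 3.417.
- vs CMHT: the largest DE is (0.55/3.417)^2 / 0.025 = 1.036, an ICC of 0.036/7 = 0.005 at m = 8.
- vs VCT-only: the largest DE is [(0.70/3.417)^2 - 0.025] x 80 = 1.356, an ICC of 0.356/7 = 0.05 at m = 8.

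**4. Credit for baseline adjustment.** SAP 8.4.2.1 adjusts for the baseline score, and the stated power takes no visible credit for it. Assume a baseline-outcome correlation of 0.5, which multiplies variance by 1 - 0.25 = 0.75. With k = 10 and an ICC of 0.05 in the adjusted outcome, V = 0.75 x 2 x 1.35/80 = 0.0253; 0.55/0.1591 - 2.576 = 0.88; power 81%. If instead 0.05 is the unadjusted ICC and the baseline removes only participant-level variance, the adjusted ICC is 0.05/0.75 = 0.067, DE is 1.467 and power is about 77%.

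**5. Primary outcome power.** Take n = 72/72/36 (80/80/40 reduced by R-square 0.1), the planned reductions of 60%, 20% and 15%, and an assumed baseline prevalence of 100% or 80%. At DE 1.45, power is about 99% or 90% vs CMHT, and over 99% or 92% vs VCT-only.

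**The case against.** **Nothing shows that the ICC is materially above zero.** This stands in part. At ICC 0.01 with 10 therapists per arm, power vs CMHT is 78.4% and type I error 5.8%, both minor. A reader might infer that the standard errors are certainly too small. The documents do not support that: it depends on an ICC and a caseload they do not give. The omission itself is not conditional, and only fitting the term will show whether it matters.

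**The unit-of-analysis sentence is not an error.** This stands. A participant can be the unit of analysis in a model that also carries a therapist effect. The mixed models leave their random effects unlisted, so the accurate charge is that therapist clustering is not specified, not that it is ruled out.

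**Power may survive.** This stands for ESTEEM vs VCT-only, where the stated 80% is conservative, and partly for ESTEEM vs CMHT, because baseline adjustment can recover much of the loss. It does not settle type I error: baseline adjustment does not correct a standard error that omits remaining therapist variation.

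**Inference conditional on these providers is defensible.** CMHT is defined as care as those clinicians usually give it, and one may choose to generalize only to them. That is a reason to accept a sensitivity analysis in place of a changed primary model. It is not a reason to leave the matter out of the plan.

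**Conclusion.** The point holds in conditional form. The plan has two therapist-delivered arms and one without therapists, and it makes no allowance for shared therapists in analysis or power. For ICC 0.02-0.05 and 16 down to 5 therapists per arm, both assumed, nominal 5% becomes about 6-14% for ESTEEM vs CMHT and about 5-8% for ESTEEM vs VCT-only. The 0.55 power figure has almost no slack: unadjusted, with 10 therapists per arm, it is about 75% at ICC 0.02 and 65% at 0.05. The 0.70 figure stays at about 79-80% at ICC 0.05 with 10 therapists per arm.

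Two stronger readings are not supported. One is that both secondary power figures are overstated; the VCT-only figure is not, on its own inputs. The other is that the primary analysis is underpowered; under the planned reductions and the assumed prevalences it keeps about 90% or more at a design effect of 1.45. For the primary comparisons the exposure is type I error and interval width.

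The design-effect figures ignore unequal caseloads and the degrees of freedom lost with few therapists, both of which would make the power loss larger.

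**What to change.** **SAP 8.3 and 8.4.** Prespecify a partially nested analysis: a therapist random effect in ESTEEM and CMHT only, with small-sample degrees of freedom. Where a marginal model is used, such as the modified Poisson fallback, use therapist-clustered variance with a small-sample correction. At minimum, make this a sensitivity analysis for ESTEEM vs CMHT.

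**Grouping rule.** To stay within intention to treat, group participants by first assigned therapist whatever happens later, and treat anyone who never had a therapist as a singleton. VCT-only participants are singletons throughout.

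**Reporting.** Give the number of therapists per arm and site, and the estimated ICC for each outcome.

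**SAP 6.3.** State that the power figures assume no therapist clustering, and give the 0.55 power over ICC 0 to 0.05. With 10 therapists per arm, unadjusted, it runs 81.7% (ICC 0), 78.4% (0.01), 75.2% (0.02) and 66.2% (0.05).

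**Cost.** SAP wording and modest modelling. The per-session surveys should allow participants to be linked to therapists, though the documents do not describe a therapist identifier. Intervals will widen, appreciably if therapists are few: with 5 per arm (about 8 degrees of freedom) the 95% critical value alone rises from 1.96 to 2.31, about 18%. The therapist variance would then be imprecisely estimated. An extra variance component also makes non-convergence of the log-binomial mixed model more likely, so the fallback in 8.3.1 should say how therapists are handled there.

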8.2 Comparability of Treatment Groups

To determine randomization effectiveness, differences in baseline demographic characteristics will be assessed between ESTEEM, CMHT, and VCT-only groups using appropriate graphical and statistical methods including summary statistics. The randomization is designed to produce balance on important covariates. If we find imbalance on key covariates, we will consider sensitivity analyses that adjust for those covariates. Study site will be included as a covariate in all analyses because randomization was stratified by study site.

STATISTICAL ANALYSIS PLAN

8.3 Analysis of Primary Outcome: HIV-Risk Behavior (Condomless Anal Sex)

8.3.1 Primary Analysis of Primary Outcome: Condomless Anal Sex

Analysis	Primary analysis of primary outcome: condomless anal sex in the absence of either PrEP or known undetectable viral load of HIV+ primary partners, measured with the TLFB, a semi-structured interview.
Analysis population	All enrolled participants
Endpoint	8-month as reported on TLFB
Unit of analysis	Participant
Method of analysis*	Generalized linear mixed model with a log (log-binomial) link using a contrast to test the comparison at the primary time point of 8 months adjusting for site and race/ethnicity (Wacholder 1986). We will conduct the comparison of ESTEEM versus VCT at 0.05 level; only if this test is statistically significant will we test ESTEEM versus CMHT at 0.05.
Handling of missing data	MAR assumption
Adjustment covariates	Study site (NYC or Miami).
Type I error	5% (2-sided)
Control of type I error	We will use a gatekeeping strategy. If the first comparison is significant at 0.05, then we will conduct the second comparison at 0.05.
Treatment effect estimate	Risk ratio with 95% confidence limits

*If the log-binomial approach fails to converge, we will use a modified log-Poisson model (Zou 2004).

Sensitivity analysis: This will only be conducted if baseline imbalance of covariates is found (see Section 7.2). Adjustment for baseline covariates not balanced at randomization.

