Participants who are deemed eligible based on the phone screener will then be invited to the office for a baseline 1 appointment. During this appointment, participants will complete a written consent. After the baseline 2 appointment, participants will be randomized to either the ESTEEM intervention, CMHT, or VCT.

During phone and in-office consent, a trained staff member will review the consent form in person, including details of the full study and study risks and precautions against risk. Participants who choose to participate in the remainder of the study will be asked to sign the consent form in the presence of the staff member (in-office) or provide verbal consent (phone screen).

We will select video clips from approximately 12 total sessions delivered to approximately five currently and formerly enrolled study participants. These videos do not contain participants' faces or identifiable information other than participants' voice and therapists' image and voice. Selected participants who have completed ESTEEM therapy will be contacted prior to completion of the study or after completion of the study in order for us to gain consent to present small portions of their therapy videos during future professional trainings at community-based clinics and agencies. Participant will be contacted by either an ESTEEM therapist or a research team member. The research team member or therapist will clearly explain that videos will only be used for instructional purpose to train community clinicians and future trainees on the ESTEEM therapy protocol. They will also be reminded in that videos do not include the participant's face or any identifiable information, only their voice and the therapist's face and voice. The therapist or research team member will explicitly state that the participant is free to decline or to ask any questions about the purpose of this request. Newly recruited participants will be able to note on the informed consent form whether or not they consent to have a small selection of their therapy recording used in the future for new therapist trainings.

CMHT therapists will provide written consent prior to providing therapy to their first participant.

7. **Evaluation of Participant(s) Capacity to Provide Informed Consent/Assent:** Indicate how the personnel obtaining consent will assess the potential participant's ability and capacity to consent to the research being proposed, if applicable

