**Confidentiality & Security of Data:**

1. What participant information will you be collecting?

The full packet of study measures and assessments is attached to this application. We propose to collect information about participants' general mental health status; HIV risk; demographics; HIV status; chlamydia and gonorrhea infection; experiences with stigma-related stress; depression and anxiety; cognitive, affective, and interpersonal functioning (e.g., rumination, social support, impulsivity, assertiveness); mental health treatment history and perspectives; substance use; sexual compulsivity; and perceptions of intervention helpfulness. We will also video tape-record all intervention sessions. Counselors will also complete session notes. Each participant will have a binder that contains all session notes. No name will be attached to the binder, only participant ID. The binders will be locked in a filing cabinet.

Participants will provide the following data at baseline and 4-, 8-, and 12-month follow-up appointments: (1) quantitative assessments, previously used with young gay and bisexual men, of mental health, substance use, and stigma-related stress, (2) interviewer-administered timeline follow-back of HIV risk behavior, including condomless anal, sex while under the influence of drugs or alcohol, PrEP use and adherence, and number of sexual partners, during the previous 3 months, (3) interviewer-administered mental health assessment with the Mini-International Neuropsychiatric Interview (MINI), (4) OraSure rapid HIV 1/2 antibody test (at baseline and 12-month follow-up), (5) urine sample and rectal and oral swabs for chlamydia and gonorrhea testing (at baseline and 12-month follow-up), and (6) engagement in the intervention.

Participants who complete remote assessments will be asked to provide their address to research staff to aide in establishing contact with the nearest emergencies services, if necessary. This information will be stored in a password protected contact database on secure Box only accessible to research staff. Once addresses are stored in the database, any emails containing identifiable participant information will immediately be hard deleted from study inboxes.

2. Will any of the following identifiers be collected?

- Names
- All geographic subdivisions smaller than a State, including: street address, city, county, precinct, zip codes
- Telephone numbers
- Fax numbers
- E-mail addresses
- Social Security numbers

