Primary Analysis	We will use a fixed sequence procedure (gatekeeper strategy) to control for multiple testing of the primary comparisons: reduction in condomless anal sex in ESTEEM vs. VCT-only and ESTEEM vs. CMHT. We will conduct the comparison of ESTEEM versus VCT-only at the 0.05 level. If we find statistical significance between ESTEEM vs. VCT-only, then we will test the second comparison ESTEEM vs. CMHT at 0.05. To make use of all data collected, we will analyze the condomless anal sex outcome using a generalized linear mixed model with a logit link using a contrast to test the comparison at the primary time point of 8 months adjusting for site.
Secondary Outcomes	Depression severity, anxiety, drug abuse, alcohol abuse, mental health diagnoses, suicidality, minority stress and universal stress processes

STATISTICAL ANALYSIS PLAN

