8.3.2 Supportive Analysis of the Primary Outcome: Number of Condomless Anal Sex Acts

STATISTICAL ANALYSIS PLAN

Analysis	Supportive analysis of primary outcome: number of condomless anal sex acts in the absence of either PrEP or known undetectable viral load of HIV+ primary partners, measured with the TLFB, a semi-structured interview.
Analysis population	All enrolled participants
Endpoint	8-month as reported on TLFB
Unit of analysis	Participant
Method of analysis*	Generalized linear mixed model with a log link (Poisson model) using a contrast to test the comparison at the primary time point of 8 months adjusting for site and baseline number of sex acts. We will conduct the comparison of ESTEEM versus VCT at 0.05 level; only if this test is statistically significant will we test ESTEEM versus CMHT at 0.05.
Handling of missing data	MAR assumption
Adjustment covariates	A priori covariates include: study site (NYC or Miami); baseline number of sex acts
Type I error	5% (2-sided)
Control of type I error	We will use a gatekeeping strategy. If the first comparison is significant at 0.05, then we will conduct the second comparison at 0.05.
Treatment effect estimate	Risk ratio with 95% confidence limits

*We will assess for overdispersion. If there is a large amount of overdispersion, we will correct the Poisson model to take this into account. We will also assess for zero-inflation. If there are excess zeros, we will use a zero-inflated Poisson model.

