8.4.1 Condomless anal sex at 12 months (binary and count)

These outcomes will follow the same methodology outlined above for the primary outcome.

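### The primary binary model has no baseline risk-behaviour covariate and is stated with two links and two covariate lists; one amendment can fix both, for a modest gain in precision

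*SAP*

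**What the plan says.** - **SAP 8.3.1, method row.** Log-binomial mixed model with a "contrast to test the comparison at the primary time point of 8 months adjusting for site and race/ethnicity".
- **SAP 8.3.1, covariate row.** It reads "Study site (NYC or Miami" and lists nothing else.
- **SAP Study Summary, Primary Analysis.** A "generalized linear mixed model with a logit link using a contrast to test the comparison at the primary time point of 8 months", adjusted for site only.
- **SAP 8.3.1, footnote.** "If the log-binomial approach fails to converge, we will use a modified log-Poisson model".
- **SAP 8.4.1 (12-month outcomes).** "These outcomes will follow the same methodology outlined above for the primary outcome", so the 12-month binary analysis inherits the same model.
- **SAP 8.3.2 (act counts).** The covariates fixed in advance are "study site (NYC or Miami); baseline number of sex acts". SAP 8.4.2.1 likewise adjusts the continuous outcomes for the baseline score.
- **Protocol, Section VI.** Data taken at baseline and at each follow-up include the "interviewer-administered timeline follow-back of HIV risk behavior, including condomless anal, sex while under the influence of drugs or alcohol".
- **Protocol, Section V, consent process.** "After the baseline 2 appointment, participants will be randomized to either the ESTEEM intervention, CMHT, or VCT", so that baseline count precedes allocation.
- **SAP 8.2 and 8.3.1, sensitivity analysis.** Other baseline covariates enter only if imbalance is found, and the comparability check in 8.2 is described for demographic characteristics.

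**The concern.** There are two defects in the same few lines.

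First, two analysts could both follow this SAP and fit different primary models: logit or log, with or without race/ethnicity. The gated test of ESTEEM against VCT-only and then CMHT rests on that model.

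Second, the baseline level of the behaviour being measured is left out of the one analysis that decides the trial, while the SAP uses baseline values for its count and continuous outcomes. If the baseline count predicts the 8-month outcome, leaving it out widens the interval for the risk ratio. The imbalance-triggered sensitivity analysis does not replace it, because its use depends on the data and it is not the primary test.

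**Working it through.** **1. The specifications side by side**

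| Place in SAP | Link | Covariates |
|---|---|---|
| Study Summary | logit | site |
| 8.3.1 method row | log | site, race/ethnicity |
| 8.3.1 covariate row | not stated | site |
| 8.3.2 (count) | log, Poisson | site, baseline acts |
| 8.4.2.1 (continuous) | linear | site, baseline score |

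**2. Which baseline variable.** Eligibility requires at least one at-risk act in the past 90 days and no adherent PrEP use. A baseline yes/no version of the outcome is therefore almost always yes and carries little information. Only the number of acts varies.

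**3. The plan's own figure.** SAP 6.2 gives reductions of 60%, 20% and 15%, R-square 0.1, two-sided 5%, at least 90% power, and 80/80/40 evaluable. It states no reference rate. From an assumed 100% baseline the risks are 0.40, 0.80 and 0.85. With B the ESTEEM share, P1 the control risk and P2 the ESTEEM risk:

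N = [1.960·√(P̄(1−P̄)/B) + 1.282·√(P1(1−P1) + P2(1−P2)(1−B)/B)]² / [(P1−P2)²(1−B)(1−0.1)]

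- CMHT, B = 1/2, P̄ = 0.60: (1.358 + 0.811)² / (0.08 × 0.9) ≈ 65.3, or about 33 per arm.
- VCT, B = 2/3, P̄ = 0.55: (1.194 + 0.638)² / (0.0675 × 0.9) ≈ 55.2, or about 37 + 19.

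So 80/80/40 is not reproduced, but at least 90% is true as a bound: power at 80/80/40 is about 99.9% for both comparisons. A reference rate of 0.71 (risks 0.284 and 0.60) would give 80.2 + 40.1 for VCT, but the documents do not state that rate. The allowance for loss reproduces: 80/0.8 = 100 and 40/0.8 = 50.

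**4. Gain in precision (simulated).** Assumptions: 100/100/50 randomized; visits at 4, 8 and 12 months; logit random intercept with SD 1.5; baseline count 1 + negative binomial (mean 7, shape 0.8); 20% loss after month 4, related to the 4-month outcome and the count. The correlation r between count and outcome in the ESTEEM arm is assumed. Relative interval width is √(1 − fall in variance).

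| r | Fall in variance of log risk ratio | Interval narrower by |
|---|---|---|
| 0 | change of about 1% or less | about nil |
| 0.15 | 1–4% | 0.5–2% |
| 0.30 | 11–14% | 6–7% |
| 0.45 | 20–24% | 11–13% |

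Monte Carlo error on the falls is about 1.5 to 2.5 points. At r = 0.30 and plan rates the fall is 7–9% if loss ignores the count, and 5–10% with random-intercept SDs of 0.75 and 2.5. A second simulation (intercept SD 1.2, loss at random, 250 runs per scenario) raised the squared mean test statistic by 6–8% at a middle strength of association and 11–18% at the strongest.

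**5. Power, logit mixed model**

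| Risks ESTEEM/CMHT/VCT | r | VCT gate | CMHT |
|---|---|---|---|
| 0.60/0.80/0.85 (assumed) | 0.15 | 87.5 → 88.4% | 79.2 → 80.3% |
| same | 0.30 | 88.7 → 92.1% | 81.5 → 85.5% |
| same | 0.45 | 89.1 → 93.6% | 82.5 → 88.6% |
| 0.55/0.70/0.75 (assumed) | 0.30 | 62.8 → 66.2% | 48.8 → 54.7% |

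At 0.40/0.80/0.85 power was at least 99.8% already. The second simulation gave 98.4–99.6% without the term and 98.8–100% with it for the VCT comparison.

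**6. Why the link matters.** Under a log link, a covariate that multiplies risk by more than 1/0.85 = 1.18 (VCT) or 1/0.80 = 1.25 (CMHT) pushes the fitted risk above 1. In single-visit log-binomial fits, 5–8% failed or reached the boundary with site only. With the count the figures were 60–63%, 92–95% and over 99% at r = 0.15, 0.30 and 0.45. Separate runs put outright failure with the count at 2–14%. Most of the trouble is therefore boundary fits, which a rule triggered by non-convergence may not catch.

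**7. Null behaviour.** With all risks 0.60, the logit mixed model rejected in 4.3–5.8% of trials without the term and 4.3–5.5% with it. The log-link mixed model and the race/ethnicity term were not simulated.

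**The case against.** The strongest reply is that this is a preference with no effect on the decision. The gain rests on a correlation that no document reports. It is near zero if the count is not prognostic, and the simulation generated outcomes on the scale that favours the term. Power is already near its ceiling at the planned rates. All of this stands, and it limits the point to a modest improvement.

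It also stands that the term cannot simply be dropped into the model of 8.3.1. Step 6 shows that it would often leave a boundary fit or displace the planned estimator. A reader might infer that the change is a free extra term in the model as planned; that was shown only for the logit version.

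The count also needs a definition. Protocol Aim 1, the protocol's sample-size text and SAP 4.1 describe the at-risk act differently, so the amendment should tie the count to 4.1.

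Timing is a fair objection. The SAP is dated 9/14/2020, after the stated end of participation on 6/24/20, and SAP 7.2 says the DSMB was shown condomless-act data by arm. A reader might infer that the analysts have seen outcomes by arm. The documents do not say so: the study team saw aggregate data, and the by-arm view went to the DSMB through an unblinded statistician. A late change still has to be justified.

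None of these replies touches the conflict over link and covariates, which needs no assumption to establish.

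**Conclusion.** The concern holds as a missed gain in precision together with an inconsistent primary specification. Expect a variance lower by about 0 to 24%, depending on an undocumented correlation, and essentially no change if the count is not prognostic. At the plan's rates no gate decision changes. That rests on reading the reductions from a 100% baseline; on the unstated 0.71 reference, planned power for VCT would be about 90%, and a few points would be available there too. For example, with a 10% fall in variance, (1.960 + 1.282)/√0.90 − 1.960 = 1.457, or about 92.7%.

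Three stronger readings are not supported:
- **That the primary result is biased or invalid without the term.** Randomization protects the comparison, and the unadjusted model held its level in simulation.
- **That the trial is underpowered because 80/80/40 is not reproduced.** The mismatch reflects an unstated reference rate and has no bearing on the omitted covariate.
- **That type I error is unaffected whichever model is fitted.** It was maintained in the logit mixed model and was not checked for the log link.

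**What to change.** Make one dated, justified SAP amendment before any unblinded outcome analysis:

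1. State one link and one covariate list (site, or site plus race/ethnicity), in the same words, in the Study Summary and in both rows of 8.3.1.
2. Add log(1 + baseline past-90-day condomless anal sex acts, counted by the SAP 4.1 definition) as a covariate fixed in advance in 8.3.1, and in the 12-month binary analysis of 8.4.1.
3. Fit it in the logit mixed model of the Study Summary. Obtain the planned risk ratio by standardization: average each participant's predicted 8-month risk under each arm over the whole sample and over the random intercept, take the ratio, and use a delta-method interval.
4. Report the model without the count as a sensitivity analysis.
5. If outcomes are already unblinded, keep the primary model and report the adjusted one as supportive, labelled as such.

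Cost: one term from data already collected, a standardization step, and an amendment dated after the stated end of participation that has to be defended.
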